- **CED:** The CED is defined during the inclusion period, as the date of the 2nd, 3rd, ... or nth RTI episode during the inclusion period (see inclusion criteria in [Section 3.2.2](#)). This is also the date when a patient fulfils all the eligibility criteria. The CED can occur any time during the inclusion period. If a patient meets the eligibility criteria more than once during the inclusion period, and thereby has several candidate CEDs, the CED used in the study will be selected at random, which is one of the unbiased methods of selection of index date (29). The CED defines the end of the baseline period and the start of the initiation grace period for each included patient.

- **Baseline period:** The baseline period for each included patient is defined as the time before the CED. The minimum baseline period will be 12 months, and the maximum baseline period will be as long as data are available in each country (from January 2005 in Belgium, from January 1994, for GPs and 2017 for paediatricians, in Italy, and from January 2018 in China). The minimum baseline period of 12 months will be used for assessing the RTI rate during the baseline period and other baseline variables ([Section 3.7.4.1](#)). The maximum baseline period (all available data) will be used for selected variables, such as comorbidities (e.g., allergies, myocardial infarction, and cancer, see [Table 8](#)), since these could have occurred earlier but may not have been recorded in the data during the 12-month baseline period. Extending the 12-month baseline period for such variables is expected to improve the accurate classification of them (i.e., decreases the risk of covariate misclassification).
- **Initiation grace period:** For each included patient, a 30-day initiation grace period starting from the CED will be applied, to allow the included patients to initiate OM-85 during a reasonable period after the CED, as it is unrealistic to expect that OM-85 would in clinical practice be prescribed on the date of meeting the eligibility criteria ([28,29](#)).
- **OM-85 initiation date:** The OM-85 initiation date will be the date of the first observed prescription of OM-85 during the 30-day initiation grace period, starting from the CED. This is applicable only for the OM-85 exposure group.

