**Table 4 Inclusion Criteria**

	Inclusion Criteria	Operational Definition
1	Patient aged $\geq 1$ year of age at CED	Aged $\geq 1$ year at CED
2	Patient has $\geq 1$ RTI episodes during the 12-month baseline period prior to CED	$\geq 1$ RTI episodes within a 12-month period during the inclusion period. The CED is the date of the 2 nd , 3 rd , ... or n th RTI episode (i.e., date of fulfilling the inclusion criteria). If one patient has multiple CED during the inclusion period, the CED will be selected randomly. The definition of an RTI episode provided in Section 3.3.2.1
3	Patient has $\geq 12$ months of continuous enrolment in the database prior to CED	$\geq 12$ months of continuous enrolment in the database prior to the CED. Operationally, patients were required to have entered the database at least 12 months before the CED to be included in the study. In THIN (Belgium and Italy), this can be defined by a district variable for entry to the database: first contact date. In Inspur (China), patients are required to have records in the database at least 12 months before the CED (during the 12-month baseline period) to be eligible for inclusion
4	No record of a prescription of any bacterial lysates in the 12-month baseline period prior to CED	No record of the country-specific drug codes ( Appendix 4 ) during the 12-month baseline period

Note: CED: cohort entry date; RTI: respiratory tract infection; THIN: The Health Improvement Network.

Inclusion criterion 2 on the requirement of having  $\geq 1$  prior RTI episodes is important to apply because OM-85 is indicated for prevention of recurrent RTIs (24). However, patients in the SOC/non-user comparator group may still have fewer prior recurrent RTIs than the OM-85 group receiving preventive therapy. Therefore, prior recurrent RTIs will also be used in the PS matching of the compared exposure groups. The impact (preventive effect) of OM-85 on the recurrence of RTIs is anticipated to be higher in patients with an increased recurrence risk (35). Hence, the analyses will also be stratified by the number of RTI episodes prior to CED (see [Table 5](#)).

The inclusion of patients is not defined by sex. Sex is instead defined at CED and considered in the PS.

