**Table 8 Secondary and Exploratory Outcomes**

Objective	Outcome	Definition	Measurement
Secondary objective 1  : Baseline characteristics	Sex	
 
Biological sex
 
	
 
Dichotomous variable (male/female)
 
Measurement at CED
 

	Age	
 
Age at index date
 
	
 
Categorical variable (1 to < 6 years, ≥ 6 to < 12 years, ≥ 12 to < 18 years, ≥ 18 to < 65 years and ≥ 65 years)
 
Measurement at CED
 

	BMI	
 
BMI = weight(kg)/height(m)
 
	
 
Continuous variable
 
Measurement closest to CED, during the 12-month baseline period
 

	Type and number of previous RTI episodes	
 
URTI only (e.g., acute nasopharyngitis, acute sinusitis, acute pharyngitis, acute tonsillitis)
 
LRTI only (e.g., whooping cough, pneumonia, acute bronchitis)
 
Other RTIs only: RTI not classified as upper or lower
 
Combination of URTI, LRTI, and/or Other RTIs
 
	
 
Categorical variable (diagnosis-related ICD-9/ICD-10 code, Appendix 3)
 
Continuous variable (number of URTIs, LRTIs, Other RTIs, URTI/LRTI/Other RTIs combined)
 
Measurement in the 12-month baseline period
 

	Comedications	
 
LABA, LAMA, ICS, LABA/ICS, LABA/LAMA, LABA/LAMA/ICS, antiallergic agents, leukotriene receptor antagonists, symptom relievers, systemic corticosteroids, systemic oral corticosteroids, influenza vaccines, influenza antivirals defined using country-specific drug codes (ATC, AIC, Other) (Appendix 4)
 
	
 
Binary variable (yes/no for each class of medication prescribed)
 
Continuous variable (number of prescriptions, length of treatment in days)
 
Measurement in the 12-month baseline period
 

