### 3.3.3 Other Variables

Selected baseline variables described under outcomes ([Section 3.3.2.2](#)) will be assessed in the Step 1 analysis and will be used for controlling for confounding at baseline, through including the selected variables to the PS and matching OM-85 initiators to non-initiators (SOC/non-user group) using the PS. The following baseline variables will be considered in the PS:

- Patient demographics: Age and sex
- BMI
- RTI history, including type (Upper/Lower/Other) and number of previous RTI episodes
- Comedications
- Antibiotic prescriptions
- Selected comorbidities, especially smoking and respiratory conditions, such as asthma, COPD, and CB
- Overall and RTI-specific healthcare resource utilisation, especially duration of RTI-related hospitalisation(s) as a proxy for severity of prior RTIs
- Calendar year of CED

The confounders applied in the PS will be detailed in the SAP.

Variables used for defining sub-populations are described in [Section 3.2.2.3](#).

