### **3.4.1 The Health Improvement Network: Belgium and Italy**

THIN® is a large European database of fully anonymised, non-linkable and non-extrapolated Electronic Health Records collected at the physicians' level. These anonymised patient-level data are obtained from a network of voluntary physicians. In Belgium and Italy, no ethics submission is needed for the current study. An ethics submission to access data from THIN is mandated in case study results will be published. In such case, THIN will submit an ethical application via the THIN Euroboard.

THIN Belgium covers information from GPs and has information on > 500,000 patients per year, with an average follow-up of 9 years. THIN Italy covers information from GPs and has information on > 550,000 patients per year, with an average follow-up of 7 years. The feasibility assessment found that overall, the variables required to address the primary objectives are well captured and of good completeness in both THIN Belgium and THIN Italy, with the exceptions of vaccine administration, lung function tests, and hospitalisation data. Lung function data will therefore not be collected, and vaccination data will be limited to influenza vaccinations. As information is collected from GPs only, the information on healthcare resource utilisation is not complete. Date of birth is captured as year of birth and therefore age in the first year of life cannot be assessed with further granularity than this.

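### Previous RTI episodes enter the propensity score as a 12-month count only; if OM-85 prescribing follows longer-run RTI burden, matching can leave a bias against OM-85

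*Protocol*

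**What the plan says.** Section 3.2.1 sets the general rule for baseline variables: "The minimum baseline period of 12 months will be used for assessing the RTI rate during the baseline period and other baseline variables". That sentence points to the descriptive baseline section (3.7.4.1), so it does not by itself define the PS. The link to the PS comes from two other places. Table 8, in the row for type and number of previous RTI episodes, gives "Measurement in the 12-month baseline period". Section 3.3.3 says that selected Table 8 variables "will be used for controlling for confounding at baseline, through including the selected variables to the PS", and its list includes "RTI history, including type (Upper/Lower/Other) and number of previous RTI episodes" with no other window.

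For other variables the protocol looks further back: "The maximum baseline period (all available data) will be used for selected variables, such as comorbidities". Its stated reason is more accurate classification. Table 8 leaves the choice between 12 months and all available data to the SAP for comorbidities, but not for RTI history.

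The text after Table 4 expects an imbalance: "patients in the SOC/non-user comparator group may still have fewer prior recurrent RTIs than the OM-85 group receiving preventive therapy". It gives this as the reason for including prior RTIs in the matching.

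The final covariate set is still open: "The confounders applied in the PS will be detailed in the SAP".

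**The concern.** A one-year count is a noisy measure of a patient's underlying RTI rate. Suppose two patients each had three episodes last year, and one comes from a group with a higher long-run rate. That patient's expected rate next year is higher, because the other patient more often had a chance bad year. If prescribers of a prophylactic respond to a longer history than the last 12 months, this difference remains after matching on the 12-month count. Matched SOC patients would then fall back further than OM-85 patients with no drug effect at all, and the primary objective 2 rate ratio would move upwards. The two groups could have identical 12-month counts, so a balance table would look perfect. The planned stratification by prior RTI episodes uses the same 12-month count and would not reveal it either.

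**Working it through.** **The protocol's own figure.** The only precision figure is in Table 9, for primary objective 1. With 2 episodes per person-year, 350 person-years per group and a rate ratio of 0.9, b = 2 × 350 = 700 and a = 0.9 × 700 = 630. The F-quantile interval in Section 3.5 then has width 0.197, as printed, and all 32 cells of the table reproduce to three decimals. No stated figure concerns the matched comparison. Table 9 serves here only to show that the protocol regards 0.9 as a small effect.

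**Check 1: closed form.** Assumptions, none of them in the protocol: each patient has a stable rate; rates are gamma distributed with shape k and mean m1 (OM-85 source) or m0 (SOC source); counts are Poisson; matching is exact on the count x over H years; there are no other PS covariates.

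- Expected rate given x: (k + x) / (k/m + H).
- OM-85 to SOC ratio at equal x: (k/m0 + H) / (k/m1 + H), which does not depend on x.

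| k | m1 vs m0 | H = 1 | H = 2 | H = 3 |
|---|---|---|---|---|
| 1 | 3 vs 2 | 1.500/1.333 = 1.125 | 2.500/2.333 = 1.071 | 3.500/3.333 = 1.050 |
| 1 | 3 vs 1.5 | 1.667/1.333 = 1.250 | 2.667/2.333 = 1.143 | 3.667/3.333 = 1.100 |

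Over shapes 0.5 to 2 and means from 2.5 vs 2 to 3 vs 1.5, the one-year ratio runs from (0.25 + 1)/(0.20 + 1) = 1.04 (k = 0.5, 2.5 vs 2) to (1.333 + 1)/(0.667 + 1) = 1.40 (k = 2, 3 vs 1.5).

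**Check 2: simulation of the prescribing mechanism.** The closed form presupposes that the groups differ in underlying rate. The simulation instead generates treatment from history, with no drug effect. Assumptions: 1,000,000 patients per scenario, at least one episode in the last year, mean rate 1 or 2 per year, k from 0.5 to 4, about 3% treated, chance of OM-85 proportional to history to the power 0.5 or 1, exact matching on the RTI count.

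| OM-85 prescribing follows | Rate ratio, 1-year matching | Rate ratio, 3-year matching |
|---|---|---|
| Last-year count | 1.00 | 1.00 |
| Three-year count | 1.05 to 1.15 | 1.00 |
| Long-run rate | 1.08 to 1.29 | 1.03 to 1.14 |

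The first row is exact for a simple reason. If treatment depends only on x, then within a level of x it is independent of the underlying rate, and there is nothing to correct.

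**Scale.** A residual ratio of 1.10 would turn a true 0.90 into 0.90 × 1.10 = 0.99.

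**The case against.** The strongest reply is that the PS covariates are left to the SAP, so nothing is final. That stands for which variables are chosen. It does not fully answer the point, because Table 8 fixes how RTI history is measured and defers only the comorbidity look-back.

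The second reply is that the bias is conditional. This stands. A reader might infer that matched SOC patients will regress further than OM-85 patients, so that the comparison is biased as planned. The protocol does not support that. It says only that SOC patients may have fewer prior RTIs, which is the measured imbalance that matching is meant to remove. It neither states nor excludes that prescribers act on more than the last 12 months.

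Third, the PS candidates also include antibiotics, comedications, respiratory conditions and healthcare use, and some of these carry information on long-run RTI burden. This stands and would shrink the figures above, which rest on the count alone. The assumption of stable rates is also untested, notably in growing children, who are most of the OM-85 patients in Inspur.

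Fourth, longer history is not available for everyone. THIN Belgium is described "with an average follow-up of 9 years" and Italy with 7 years. A reader might take these as the look-back available before cohort entry, but they are total time in the database. Entry needs only 12 months of enrolment. Italian paediatrician records start in 2017. Inspur data start in January 2018, so months 13–24 are not fully observed for any 2019 entry, which is 12 of the 42 inclusion months. A uniform 12-month window is therefore defensible as the core covariate. It does not follow that earlier history should be ignored where it exists.

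Finally, the protocol acknowledges residual confounding and a heterogeneous comparator in general terms. Its visible text does not address this mechanism.

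**Conclusion.** The point holds in conditional form. Table 8 and Section 3.3.3 together carry a 12-month RTI history into the PS, while the protocol's own argument for longer look-back is applied to comorbidities and not to the history of the primary outcome. If prescribing reflects RTI burden beyond that year and beyond the other PS covariates, with OM-85 patients carrying the heavier burden, the primary objective 2 rate ratio is biased against OM-85 and balance on the 12-month count will not show it. The residual is about 1.04 to 1.40 in the closed form and 1.05 to 1.29 in the simulation. Both rest on assumed means, shapes and prescribing rules and on matching on the count alone. The residual is 1.00 if prescribing follows only the 12-month count. This is an inexpensive improvement to confounding control. It does not show that the planned comparison is wrong, and in the direction described it could hide a benefit but not create one.

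Separately, the objective statement in the synopsis describes recurrent RTIs over 24 months for Inspur and without limit for THIN, while Section 2, Table 4 and Table 8 use 12 months. These passages need reconciling in any case.

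**What to change.** - Keep the 12-month RTI count in the PS.
- Add the RTI count or rate in months 13–24 and 25–36 before the CED in THIN, and in months 13–24 in Inspur where observed, with an indicator for look-back not observed.
- Report balance on these earlier counts before and after matching, by country.
- Repeat primary objective 2 in THIN patients with at least 36 months of history before the CED, as a sensitivity analysis.
- State one look-back for RTI history in the synopsis, Section 2, Table 4 and Table 8, and say which window applies to eligibility and which to the PS.

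The cost is a change to Table 8 and the SAP wording plus a few derived variables; no new data source is needed. The downside is incomplete earlier history for patients with short enrolment, Italian paediatric patients, Inspur entries in 2019 and very young children. The not-observed indicator will track age, calendar time and date of database entry; age and calendar year are already PS candidates. The 36-month subset is a selected population, so it supports the main analysis and does not replace it.

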**Table 2 Events Ending Follow-up and Censoring Variables**

		Operational Definition
Events ending follow-up, throughout the follow-up		
1	End of 24-month follow-up	2 years from end of initiation grace period for each patient
2	Death	For THIN Italy and Belgium: last contact date, which defines exit from the database regardless of reason (death, physician change, or choosing to exit the database) For Inspur China: Date of death directly available by a report from social security sent to Inspur
3	Loss to follow-up/exit of data source	For THIN Italy and Belgium: last contact date, which defines exit from the database regardless of reason (death, physician change, or choosing to exit the database) For Inspur China: Date of lost to follow-up, which defines exit from the database regardless of reason (death or migration to another city)
Censoring during follow-up, after the 30-day initiation grace period: deviation from the assigned treatment strategy		
1.1	OM-85 group: None	-
1.2	SOC/non-user group: at first date of OM-85 prescription during follow-up (after the initiation grace period)	Same
1.3	Sensitivity analysis: The SOC/non-user group are censored at the first date of prescription for any bacterial lysate (including OM-85), the OM-85 group would be censored at the first date of prescription of any bacterial lysate other than OM-85 during follow-up	Same

Note: CED: cohort entry date; SOC: standard of care; THIN: The Health Improvement Network.

### 3.2.2 Study Population

The overall study population will include patients  $\geq 1$  year of age with  $\geq 1$  RTI episodes and no prescriptions of bacterial lysates within 12 months prior to inclusion to the study. Additionally, included patients will be required to have  $\geq 12$  months of continuous enrolment in the database prior to inclusion. The inclusion criteria are detailed in [Table 4, Section 3.2.2.1](#). No exclusion criteria are applied for this study.

The CED is the date of the 2nd, 3rd, ... or nth RTI episode, i.e., the date of fulfilling this inclusion criterion. During the inclusion period, patients can have several CEDs. For patients with several CEDs, the CED of the patient used in the study will be selected randomly, which is one of the unbiased methods to select the date (29). Thus, each patient can enter the study only once.

Patients in the overall study population will be categorised to one of the two exposure groups (treatment strategies): patients who initiated OM-85 at the CED or during the 30-day initiation grace period, and SOC/non-user group of patients who did not initiate OM-85 at the CED or during the 30-day initiation grace period.

The primary and secondary objectives and the exploratory objectives **CCI** will be studied in the overall study population ([Table 3](#)). The exploratory objectives **CCI** **CCI** **CCI**. The sub-populations applied in this study are further described in [Section 3.2.2.3](#).

**Table 3 Populations for Each Study Objective**

Objective		Population In Which Studied and Index Date
Primary objectives		
1	RTI rate 12 months before and 12 and 24 months after initiating OM-85	
 
OM-85 initiators only, within the overall study population
 
Index date: OM-85 initiation date
 

2	Comparative effectiveness – rate of RTI episodes during follow-up at 12 and 24 months	
 
Both exposure groups (OM-85 initiators and SOC/non-user group) within the overall study population
 
Index date: end of initiation grace period
 

Secondary objectives		
1	Patient characteristics at CED	
 
Both exposure groups (OM-85 initiators and SOC/non-user group) within the overall study population
 
Index date: CED
 

2	Descriptive pattern of prescribing OM-85	
 
OM-85 initiators only, within overall study population
 
Index date: OM-85 initiation date
 

3	RTI rate 12 months before and 6 and 9 months after initiating OM-85	
 
OM-85 initiators only, within the overall study population
 

Objective		Population In Which Studied and Index Date
		
 
Index date: OM-85 initiation date
 

4	Comparative effectiveness – rate of RTI episodes during follow-up at 6 and 9 months	
 
Both exposure groups (OM-85 initiators and SOC/non-user group) within the overall study population
 
Index date: end of initiation grace period
 

5	Descriptive pattern of prescribing antibiotics during follow-up	
 
Both exposure groups (OM-85 initiators and SOC/non-user group) within the overall study population
 
Index date: end of initiation grace period
 

6	Descriptive pattern of concomitant medications of interest during follow-up	
 
Both exposure groups (OM-85 initiators and SOC/non-user group) within the overall study population
 
Index date: end of initiation grace period
 

7	Descriptive healthcare resource utilisation during follow-up	
 
Both exposure groups (OM-85 initiators and SOC/non-user group) within the overall study population
 
Index date: end of initiation grace period
 

Exploratory objectives		
1	CCI [REDACTED] CCI [REDACTED] CCI [REDACTED]	CCI [REDACTED] CCI [REDACTED] CCI [REDACTED] CCI [REDACTED]
2	CCI [REDACTED] CCI [REDACTED] CCI [REDACTED]	CCI [REDACTED] CCI [REDACTED] CCI [REDACTED] CCI [REDACTED] CCI [REDACTED]
3	CCI [REDACTED] CCI [REDACTED] CCI [REDACTED]	CCI [REDACTED] CCI [REDACTED] CCI [REDACTED] CCI [REDACTED] CCI [REDACTED]
4	CCI [REDACTED] CCI [REDACTED]	CCI [REDACTED] CCI [REDACTED] CCI [REDACTED] CCI [REDACTED] CCI [REDACTED]
5	CCI [REDACTED] CCI [REDACTED]	CCI [REDACTED] CCI [REDACTED] CCI [REDACTED] CCI [REDACTED] CCI [REDACTED]

Objective		Population In Which Studied and Index Date
		CCI [REDACTED]
6	CCI [REDACTED] CCI [REDACTED] CCI [REDACTED] CCI [REDACTED]	CCI [REDACTED] CCI [REDACTED] CCI [REDACTED]
7	CCI [REDACTED] CCI [REDACTED] CCI [REDACTED] CCI [REDACTED]	CCI [REDACTED] CCI [REDACTED] CCI [REDACTED] CCI [REDACTED]
8	CCI [REDACTED] CCI [REDACTED] CCI [REDACTED] CCI [REDACTED] CCI [REDACTED]	CCI [REDACTED] CCI [REDACTED] CCI [REDACTED]
9	CCI [REDACTED] CCI [REDACTED] CCI [REDACTED] CCI [REDACTED] CCI [REDACTED]	CCI [REDACTED] CCI [REDACTED] CCI [REDACTED] CCI [REDACTED]
10	CCI [REDACTED] CCI [REDACTED] CCI [REDACTED] CCI [REDACTED]	CCI [REDACTED] CCI [REDACTED] CCI [REDACTED]
11	CCI [REDACTED] CCI [REDACTED] CCI [REDACTED] CCI [REDACTED] CCI [REDACTED]	CCI [REDACTED] CCI [REDACTED] CCI [REDACTED] CCI [REDACTED]

Note: CCI [REDACTED]; CED: cohort entry date; CCI [REDACTED];  
 COVID-19: coronavirus disease 2019, RTI: respiratory tract infection; SOC: standard of care.

